Note: If desired, the telephone-based surveys may be administered in hard copy. For Phase I, staff will call participants 1 month (+/- 7 days) following baseline completion to complete their follow-up survey, or mail their follow up survey at that time if requested. Several telephone reminders will be provided as needed to facilitate completion. Completion of this follow-up may occur outside of the timeframe for initial contact. Phase II follow-up will include a disposition form as well, and follow these same procedures, with staff attempting to contact participants via phone or mailing surveys 3 and 6 months (+/- 7 days) from completion of the baseline survey. For those opting for mail survey completion, staff may obtain the disposition status prior to mailing the appropriate survey within 7 days of obtaining this information. Staff may send a hard copy survey (omitting the disposition form as needed) if unable to reach them via phone, in an attempt to reduce loss to follow up. Those selected for the final telephone interview in Phase II will be contacted within 3 months of completion of their final 6 month survey (however, completion of the interview may occur outside of this timeframe based on participant scheduling needs). Three or 6 month follow-up surveys conducted via phone are conducted by a blinded staff member.

The UMN team will also determine the degree to which participants use and apply CtP recommendations. The research assistant or research coordinator will conduct a brief semi-structured telephone interview 1 month following baseline. If the participant has not completed CtP by the 1 month time-point, the participant will be considered lost to follow up, and the checklist and interview will not be administered. The research assistant or coordinator will also administer semi-structured interviews to the three CtP interventionists to obtain their perceptions when administering the tool to ADRD caregivers. These interviews will be conducted after the Phase I participants have completed CtP. The open-ended responses will provide in-depth information on facilitators to use and barriers to refine prior to Phase II. Recorded interviews will be transcribed (by Production Transcripts) for data analysis.

Phase II Procedure

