The qualitative and quantitative data available from Phase I will be employed to refine the content and delivery of CtP prior to phase II. In phase II, 100 caregivers of persons with ADRD will be enrolled. Similar to phase I, after receiving a new

PROTOCOL TITLE: Care to Plan: Preliminary Efficacy of a Tailored Resource for Family Members of Persons with Dementia

contact, the UMN team will conduct a telephone-based screening for eligibility, complete consent, and administer the baseline survey. Participants will be randomly assigned in a 1:1 ratio to receive either the CtP intervention or a usual care control condition. The UMN team will generate a random assignment schedule using <http://randomizer.org>. The research staff who will have responsibility for all follow-up data collection will not have access to the random assignment schedule, nor will they be able to determine the next treatment assignment in the sequence. The randomization procedures will ensure both random assignment as well as treatment concealment during data collection and are consistent with CONSORT recommendations. Participants in both groups will be followed for six months with data collection at baseline, three months, and six months. For Phase II, a brief disposition survey to determine the participant's caregiving status, as well as the status of the person they provide care for, will be administered (at 3 and 6 month follow up) prior to administering the appropriate survey. An embedded experimental mixed methods design will be utilized ([QUAN+qual]→qual) that will incorporate various qualitative data collection elements within and following the 6-month randomized controlled evaluation of CtP.

As of February 2021, only those with an ID number (i.e. those reviewing the tool with study interventionists) will have their CaretoPlan responses tracked. Thus, others using the tool for personal use within or outside of the context of the study will no longer have responses tracked. *Note: If it is learned that someone enrolled in the study reviewed the tool on their own prior to reviewing it with a study interventionist, this information will be tracked internally.*

As with phase I, surveys will be administered via telephone or in hard-copy surveys.

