Phase II will feature 20 telephone-based semi-structured interviews with purposively sampled caregivers who are randomly assigned to receive the CtP. These interviews will take place following completion of the final 6-month follow-up survey. A sequential mixed methods sampling approach will be utilized where the results of the first methodological strand will inform the selection of participants in this second methodological strand. Specifically, research staff will purposively select 20 caregivers who report higher and lower average system review checklist scores (indicating how well CtP met or did not meet their needs). A stratified purposive sampling approach will be applied: caregivers of

PROTOCOL TITLE: Care to Plan: Preliminary Efficacy of a Tailored Resource for Family Members of Persons with Dementia

different kin relationship, caregiver gender, and racial or ethnic background of caregivers will be identified and asked to participate. *Note: Those without checklist scores may also be interviewed as needed. Additionally, participants may be selected from the waitlist control group.* Again, recorded interviews will be transcribed (by Production Transcripts) for data analysis.

Surveys are sent within 7 days of their due date, and participants are given several reminders to facilitate survey completion as needed. If any survey is not returned, participants are still provided subsequent surveys, unless they withdraw from the study. Those selected for a final phone interview will be contacted within 2 months of completion of their final survey.

As with Phase I, the research assistant or coordinator will administer semi-structured interviews to the three CtP interventionists to obtain their perceptions when administering the tool to ADRD caregivers. In addition, semi-structured interviews will be conducted with Riverside Health collaborators to obtain their perceptions on the benefits and hindrances of implementing CtP in their healthcare system. These interviews will be conducted after the Phase II recruitment ends on 12/1/2021, and participants have completed CtP. With permission, these interviews will be recorded and professionally transcribed (by Production Transcripts) for data analysis. The open-ended responses will provide in-depth information on facilitators to use and barriers to inform future implementation possibilities of CtP.

Waitlist Control

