17.2 Power Analysis

Longitudinal analysis procedures (growth curve modeling) will be utilized to capitalize on the randomized design and the multiple waves of data that will be collected. The objective of the Phase II analyses is to generate power estimates for a subsequent, larger scale evaluation of CtP. However, a sample size of 100,

PROTOCOL TITLE: Care to Plan: Preliminary Efficacy of a Tailored Resource for Family Members of Persons with Dementia

factoring in a conservative 10% attrition rate at 6 months, would have sufficient power to detect a medium/large effect size).^{30,31} As noted in various recommendations, a sample of 20 is considered adequate for semi-structured interview protocols to ensure the richness of open-ended data collected.^{32,33}

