18.1.2 Adverse Event and Serious Adverse Event Collection and Reporting

In addition to ongoing monitoring of protocol and human subjects compliance, [name] and research team will generate safety reports annually that will list adverse events, serious events, unexpected events, events related to or associated with the intervention, and the potential causality of the intervention to the event for each participant if they occur. If the research team becomes aware of an adverse event or unanticipated problem occurring while a participant is enrolled in the study (consent through the participant's final data collection), the event will be documented and/or reported per the protocol below. Conditions existing prior to study enrollment that have not worsened/changed will not be considered adverse events and will not be documented/reported. Per the University of Minnesota IRB guidelines, all events or information that indicates a new or increased risk, or a safety issue, will be promptly reported.

Taken directly from the NIA Adverse Event and Serious Adverse Event Guidelines, the definition of each event is as follows:

Adverse event (AE). Any untoward or unfavorable medical occurrence in a human study participant, including any abnormal sign (e.g. abnormal physical exam or laboratory finding), symptom, or disease, temporally associated with the participants' involvement in the research, whether or not considered related to participation in the research.

Serious adverse event (SAE). Any adverse event that results in death; is life threatening, or places the participant at immediate risk of death from the event as it occurred; requires or prolongs hospitalization; causes persistent or significant disability or incapacity; results in congenital anomalies or birth defects; and/or is another condition which investigators judge to represent significant hazards.

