Unanticipated problem (UP). any incident, experience, or outcome that meets all of the following criteria: unexpected, in terms of nature, severity, or frequency, given (a) the research procedures that are described in the protocol-related documents, such as the IRB-approved research protocol and informed consent document; and (b) the characteristics of the study population; related or possibly related to participation in the research (in this guidance document, possibly related means there is a reasonable possibility that the incident, experience, or outcome may have been caused by the procedures involved in the research);

PROTOCOL TITLE: Care to Plan: Preliminary Efficacy of a Tailored Resource for Family Members of Persons with Dementia

and suggests that the research places participants or others at a greater risk of harm (including physical, psychological, economic, or social harm) than was previously known or recognized.

Phase II participants will be asked at 3 and 6 month follow up: “In the last three months, since your last survey, was there any new or worsening health problem that caused you to be unable to perform your daily routine (i.e. not go to work or volunteer), seek medical care (i.e. go see your doctor, go to the ER or hospital), or take a new medication?” Those medical events will be documented as adverse events. Other events that will also be considered adverse events are included below.

All AEs (following consent) will be collected on an adverse event form, in electronic format. AEs experienced by a participant during a study procedure (i.e. intervention/survey) will be reported within 5 days of discovery to the University of Minnesota IRB (per the University’s IRB procedures) and annually to the NIA in data monitoring reports.

AE that occur outside of the context of a study procedure (i.e. intervention/survey), as well as those that are determined to be not related to the participant’s involvement in the study, will be documented via the team’s electronic AE form and included in the annual report (to be shared with IRB, Safety Officer, and NIA Program Officer).

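### The scripted adverse-event question carries two recall windows that disagree after a missed or late survey, so events in months 0 to 3 may be under-ascertained

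*Combined protocol and SAP*

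**What the plan says.** Section 18.1.2 (placed under heading 19.0) fixes when the question is put: "Phase II participants will be asked at 3 and 6 month follow up". The wording begins "In the last three months, since your last survey, was there any new or worsening health problem" and then lists the consequences that make a health problem reportable. The stated intention is complete capture from consent: "All AEs (following consent) will be collected on an adverse event form, in electronic format".

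Section 5.1 sets the schedule: "Participants in both groups will be followed for six months with data collection at baseline, three months, and six months". It also provides for irregular follow-up. On missed surveys: "If any survey is not returned, participants are still provided subsequent surveys, unless they withdraw from the study". On timing, staff make contact within 7 days either side of the due date, but "Completion of this follow-up may occur outside of the timeframe for initial contact". That sentence is written for Phase I; the same paragraph says Phase II follow-up uses the same procedures.

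Apart from the scripted question, section 18.1.2 relies on staff learning of events: "If the research team becomes aware of an adverse event or unanticipated problem occurring while a participant is enrolled in the study", the event is documented or reported.

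**The concern.** The question states two periods as if they were one. They coincide for a caregiver who completes every survey on schedule. They do not coincide for one who skipped month 3, because the last survey is then baseline, six months back. They also diverge when a survey is completed late. The document does not say which period governs or give an alternative wording.

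The three-month limit comes first, and a respondent may reasonably follow it. Those who cannot be reached by telephone may be sent a paper form, so there may be no interviewer to clarify the period. This is the only scheduled prompt for medical events that the document describes. At stake is whether the safety listings and annual reports cover the whole of follow-up for people with irregular attendance.

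**Working it through.** The plan states no figure for how much of follow-up the question covers, so there is nothing to reproduce. The check is simple arithmetic.

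**Inputs**
- Length of follow-up: 6 months, with surveys at months 3 and 6 (section 5.1).
- Recall windows: three months, or back to the previous survey (section 18.1.2).
- Planned Phase II sample: 100 caregivers (sections 1.0 and 12.1), giving 100 × 6 = 600 person-months.
- *m*, the share who miss month 3 but answer month 6: **not given**. Section 17.2 offers only "factoring in a conservative 10% attrition rate at 6 months", which is loss at the end of follow-up and a different quantity. *m* is therefore an assumption, shown as a range.

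**Step 1. One caregiver who missed month 3 and answers at month 6.** Coverage = months asked about ÷ 6.
- Three-month reading: 3/6 = 50%.
- Since-last-survey reading (last survey = baseline): 6/6 = 100%.

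**Step 2. Whole sample.** Share of person-months unasked under the three-month reading = *m* × 3/6.

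| Assumed *m* | Three-month reading | Person-months of 600 | Since-last-survey reading |
|---|---|---|---|
| 5% | 2.5% | 15 | 0% |
| 10% | 5% | 30 | 0% |
| 15% | 7.5% | 45 | 0% |
| 20% | 10% | 60 | 0% |

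Only people who answer month 6 count in *m*. Those who miss both surveys are asked nothing under any wording.

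**Step 3. Timing when both surveys are done.** Three months is about 91.3 days. If each survey is completed within 7 days of its due date, the gap between them runs from 91.3 − 14 = 77.3 to 91.3 + 14 = 105.3 days. The two windows then differ by at most 14 days, or 14/182.6 = 7.7% of six months. Because completion may fall outside the contact window, the difference can be larger. A long gap leaves time unasked under the three-month reading. A short gap makes the periods overlap, so an event could be reported twice.

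**The case against.** The strongest reply is that the second phrase already does the work. For a caregiver who missed month 3, the time since the last survey runs back to baseline and covers everything. This stands in part. A reader might infer that everyone who missed month 3 reports on only half of follow-up, and the wording does not support that: half coverage is one of two readings. What remains is that the stem also states a three-month limit, and no rule ranks the two.

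Second, a reader might infer that early events are lost. That is too strong. Section 18.1.2 records any event the team learns of from consent to final data collection, and separately lists deaths, suicidal ideation, abuse or neglect, and events at the investigator's discretion. These routes are largely passive, however, and the university team has no access to medical records (sections 18.1 and 20.2), so it cannot recover unreported events from charts. They soften the gap without closing it.

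Third, a reader might infer a biased comparison between arms. Nothing shows that month-3 non-response differs by arm. Adverse events are not an endpoint in section 3.0, section 17.1 plans no between-arm analysis of them, and reporting is by listings and annual summaries.

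Fourth, the survey forms are not reproduced in the document, so a staff prompt or alternative wording for a missed survey cannot be ruled out. Reminders and mailed copies should also keep the number affected down.

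**Conclusion.** The point holds as a wording ambiguity with a possible effect on safety ascertainment. The two recall windows disagree when month 3 was missed or a survey was late, and the plan does not say which governs. For a caregiver who missed month 3, coverage is 50% or 100% depending on the reading. Across the sample, 2.5% to 10% of person-time would go unasked under the three-month reading if *m* were 5% to 20%, and none under the other. Those percentages rest on an assumed *m* and on a denominator of 100 caregivers followed for six months; the actual number affected cannot be derived from the document. The endpoint analyses do not depend on this question. The improvement is minor but worthwhile because it costs little.

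**What to change.** Replace the two opening time phrases with one anchor, *Since [date of your last completed survey, or of baseline if none since]*, and leave the rest of the question as it is. Staff fill in the date on telephone surveys, and it is pre-printed on mailed forms. Record the length of the recall period with each answer.

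Recruitment ended on 12/1/2021 and the latest listed revision is dated 4/28/23, so scheduled surveys in this cohort are probably complete. The rewording then mainly serves the larger evaluation that this study is meant to inform. For surveys already collected, use the completion dates to report how many participants answered month 6 without a month-3 survey, and how much person-time the question clearly covered under either reading.

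The cost is one wording change, a date field and a short tabulation. The downside is recall of up to six months for a few participants, with the loss of accuracy that longer recall may bring.

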14.0 Risks to Participants

Since the study involves no invasive procedures, there will be no physical risks to study participants. The consideration of need is potentially stressful, and thus there are possible psychological risks for the caregiver. However, the research team has considerable experience providing psychosocial support to dementia caregivers on various protocols and serious psychological risks are unlikely to occur based on this experience. The potential social or legal risks for the participants relate only to possible violations of confidentiality. Given the procedures outlined below, such risks are highly unlikely.

The experience of the research team and the exclusion of caregivers with serious psychiatric illness will minimize the possibility of psychological risks. The unlikelihood of such problems is evident from the absence of any clinically significant problems during

PROTOCOL TITLE: Care to Plan: Preliminary Efficacy of a Tailored Resource for Family Members of Persons with Dementia

the past 12 years that the research team has operated various protocols related to dementia caregiving intervention research. The research coordinator and research assistant will be trained to interview in ways that are non-threatening, friendly, and respectful. We will emphasize to all participants that they do not have to complete any question they do not want to answer, and that the interview may be terminated at any time according to their wishes. We will stress to ADRD caregivers that their decision to discontinue the study will in no way affect the services they are receiving from the University of Minnesota, RHS, or other entities.

In the event a caregiver does become upset during the interview process, the research coordinator or research assistant will contact [name], who will be available for consultation. If a caregiver is in crisis because of their care situation or some other reason, research staff will be instructed to consult with [name]. With the caregiver's permission, we will then contact the appropriate resource person in an external agency (e.g., the Alzheimer's Association). Based on the research team's experience working with their caregiving families, we expect very few or no such instances to occur. If a member of the research team does identify neglect or other potentially inappropriate care practices, Virginia Adult Protective Services will be notified to protect the rights of persons with dementia and their families.

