 - Medical events or emergencies: Research staff will call 911 as needed for emergencies (if during study procedure) or provide psychological support and encourage the participant to follow-up with their medical provider as needed (if occurred outside of study procedures). These medical issues (unrelated to study involvement) are considered expected, due to the nature of our study population. These events will be documented/reported as adverse events per above protocol if they meet one of the following criteria: a new or worsening health problem that causes the participant to 1) be unable to perform their daily routine, 2) seek medical care (provider visit, hospitalization, residential care placement, etc.), or 3) take a new medication. *[Note: Medical events or emergencies of a non-participant will not be considered/document as adverse events].*
 - Death of participant is reported promptly to the University of Minnesota IRB per above procedures (and is also reported to the Safety Officer and NIA within 24 hours of the team's knowledge if determined potentially related to study involvement; otherwise is included on routine annual reports shared with Safety Officer and NIA). Deaths in our study population (unrelated to study involvement), are considered expected. *[Note: Deaths of a non-participant will not be considered/document as adverse events].*
 - Suicidal ideation of participant: If participant informs study staff of thoughts of suicide, staff will discuss the concern with the participant and offer resources (i.e. [name] line, healthcare provider, etc.). Staff will ask them to provide verbal agreement not to harm themselves, and alert PI immediately. If necessary, staff will call 911. This will be documented/reported as serious adverse event.
 - Abuse/Neglect of participant: Document as adverse event per above protocol. If indicated, make vulnerable adult report to adult protective services.
 - Other events that in the discretion of the PI should be reported as adverse events.
- Not considered adverse events:

PROTOCOL TITLE: Care to Plan: Preliminary Efficacy of a Tailored Resource for Family Members of Persons with Dementia

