- If a participant scores 16 or higher on the CES-D [risk for depression], study staff will provide resources as needed (i.e. <https://www.samhsa.gov/>, healthcare provider, and Riverside/Senior Care Navigation). Mental health concerns are common in our study population and fluctuation of assessment scores is expected. Unless participant indicates a concern regarding self-harm or that the health issue has caused them to: be unable to perform their daily routine, seek medical care, or take a new medication, it will not be documented as an adverse event.
- Survey responses indicating changes in sleep, stress/anxiety, activities of daily living, or general well-being alone will not trigger an adverse event report. These concerns are common in our study population and fluctuation of assessment scores is expected. Unless participant indicates a concern regarding self-harm or that the health issue has caused them to: be unable to perform their daily routine, seek medical care, or take a new medication, it will not be documented as an adverse event.
- Routine or planned medical encounters for symptoms or conditions that are not new, worsened, or changed since enrollment, as well as those events that have not caused the participant to: be unable to perform their daily routine, seek medical care, or take a new medication, will not be documented as an adverse event.
- A physical attack or injury to participant by a non-participant (i.e. care recipient) would be documented/reported as an adverse event if the participant requires medical care. *[Note: Other potential dementia related behaviors that do not result in participant injury are not considered adverse events.]*
- Participant reports that non-participant (i.e. care recipient or person with memory impairment) displays risk-behavior (i.e. aggression/threats, comments about death or self-harm): This will not be documented as adverse event, as individual is not enrolled in the study. If participant reports concern to study staff, study staff will encourage them to follow up with healthcare provider or Riverside/Senior Care Navigation for resources.
- Suicidal ideation of non-participant (care recipient): If participant shares concern about care recipient (non-participant) suicidal ideation, study staff will talk about the concern and provide resources as requested (i.e. [name] line, healthcare provider, etc.). This is not documented as an adverse event, as individual is not enrolled in the study.

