PROTOCOL TITLE: Care to Plan: Preliminary Efficacy of a Tailored Resource for Family Members of Persons with Dementia

- Abuse/Neglect of non-participant: Document and report as an adverse event only if study participant is involved. Make vulnerable adult report to adult protective services as indicated.
- Driving with dementia/cognitive impairment (participant or non-participant): Provide resources as needed (i.e. <https://alz.org/help-support/caregiving/safety/dementia-driving>, <https://www.thehartford.com/resources/mature-market-excellence/dementia-driving>, etc.), encourage family involvement with medical provider, and adhere to local laws. This is not considered/document as an adverse event.
- Unlicensed driving (participant or non-participant): If study staff are informed that an individual is driving without a license, staff will encourage driving in accordance with local laws and explain potential consequences. This is not considered/document as an adverse event.
- Environmental/home hazards (i.e. unlocked/loaded weapons, other safety concerns): Encourage remedying this situation for safety; recommend in-home safety assessment as needed. This is not considered/document as an adverse event unless immediate risk of harm is identified (i.e. abuse/neglect).

As taken directly from the NIA Adverse Event and Serious Adverse Event Guidelines, the severity, expectedness, and relatedness of each AE and serious adverse event (SAE) will be graded as follows:

Severity

- **Mild**: Awareness of signs or symptoms, but easily tolerated and are of minor irritant type causing no loss of time from normal activities. Symptoms do not require therapy or a medical evaluation; signs and symptoms are transient.
- **Moderate**: Events introduce a low level of inconvenience or concern to the participant and may interfere with daily activities, but are usually improved by simple therapeutic measures; moderate experiences may cause some interference with functioning
- **Severe**: Events interrupt the participant's normal daily activities and generally require systemic drug therapy or other treatment; they are usually incapacitating

Expectedness

- **Unexpected** - nature or severity of the event is not consistent with information about the condition under study or intervention in the protocol, consent form, product brochure, or investigator brochure.
- **Expected** - event is known to be associated with the intervention or condition under study.

Relatedness

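### The adverse-event recording threshold is narrower than the protocol's own definition and leaves nearly all mild events, and distress below the threshold, outside the log

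*Combined protocol and SAP*

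**What the plan says.** Section 18.1.2 takes its definition of an adverse event from the funder's guidelines: "Any untoward or unfavorable medical occurrence in a human study participant, including any abnormal sign", symptom or disease, whether or not related to the research. There is no requirement that the event have any consequence.

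The operating rules later in 18.1.2 are narrower. Medical events are documented if they are "a new or worsening health problem that causes the participant to 1) be unable to perform their daily routine, 2) seek medical care", "or 3) take a new medication". The question put to Phase II participants at 3 and 6 months has the same filter built in: "was there any new or worsening health problem that caused you to be unable to perform your daily routine", or to obtain care or take a new drug. The list of things not counted as adverse events includes routine encounters, "as well as those events that have not caused the participant to: be unable to perform their daily routine, seek medical care"; a new drug is the third trigger there too. The same list states: "Survey responses indicating changes in sleep, stress/anxiety, activities of daily living, or general well-being alone will not trigger an adverse event report". A CES-D score of 16 or more is treated in the same way. Both of these exclusions lift if the caregiver indicates a self-harm concern or meets one of the three criteria.

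The severity scale, also in 18.1.2, describes a Mild event as "easily tolerated and are of minor irritant type causing no loss of time from normal activities", with no need for therapy or medical evaluation.

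Section 14.0, repeated in 18.1.1, names the risk to participants apart from confidentiality: "The consideration of need is potentially stressful, and thus there are possible psychological risks for the caregiver".

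**The concern.** One section holds a broad definition, a narrow recording rule and a three-grade severity scale, and these do not fit together. If staff follow the rule, the lowest grade is almost never used and the log does not represent the events the definition covers.

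The filter also falls on the harm the protocol itself considers possible. A caregiver distressed by going through the CtP assessment, but who keeps functioning and does not seek care, fits the named risk and fits no listed recordable category. An unrelated clinic visit for a new problem is recorded. Section 18.2.0 says the project is meant to inform a larger randomized trial. A low or zero count of related events could be carried forward as reassurance it does not provide.

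**Working it through.** No safety figure is stated, so there is nothing to reproduce. The check sets the rules of 18.1.2 side by side and traces a distress episode through them.

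**Step 1: definition against recording rule.** The definition needs only an untoward sign, symptom or disease in temporal association with the study. The rule adds one of three consequences. Any event with none of the three satisfies the definition and fails the rule.

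**Step 2: recording rule against the Mild grade.**
- Criterion 1 (daily routine stopped) and Mild (no time lost from normal activities) cannot both hold.
- Criterion 2 is care that was sought, while Mild concerns evaluation that was required. They can coexist, for example when a transient symptom prompts a visit that proves unnecessary.
- Criterion 3 is a drug that was taken, while Mild concerns therapy that was required. The same reasoning applies.

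The Mild grade is therefore nearly empty for medical events, but not strictly empty. Some Moderate events can also be missed, since that grade allows partial interference with activities short of inability.

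**Step 3: routes to the log for sub-threshold distress from a session or survey.**
- Follow-up question: carries the same threshold.
- Survey scores: excluded when they stand alone.
- Suicidal ideation (a serious adverse event) and abuse or neglect of the participant: recorded without the threshold, but these are different events.
- Five-day IRB reporting of events during a study procedure: applies to events already classed as adverse events.
- Duty to report new or increased risk, and the unanticipated-problem definition: a poor fit for a risk already named in 14.0.
- Consultation when a caregiver becomes upset in an interview or is in crisis (14.0 and 18.3.1): an escalation step, not a recording rule.
- PI discretion: available, but without criteria.

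Only the last leads to the log.

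**Step 4: what a zero count would mean.** With 100 caregivers randomized 1:1, the CtP arm has 100 / 2 = 50. For 0 of 50, the exact two-sided 95% upper limit is 1 − 0.025^(1/50) = 0.071, or 7.1%. That limit applies to events the rule records. It places no bound on events the rule leaves out. Purely as an assumption, true rates of sub-threshold distress from 2% to 20% would mean 50 × 0.02 = 1 to 50 × 0.20 = 10 affected caregivers. Any of these is compatible with a recorded count of zero if PI discretion is not used. The documents do not say where in that range, if anywhere, the rate lies.

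**The case against.** A reader might infer that no recorded event can ever be mild, that the psychological risk is excluded outright, or that CtP must come out harmless by construction. The documents support none of these.
- A precautionary visit for a trivial symptom is recordable and can be graded Mild.
- Psychological events are thresholded. They are recorded with a self-harm concern, loss of routine, care-seeking or new medication, and suicidal ideation is recorded regardless.
- Section 3.2 makes role captivity, role overload, loss of intimate exchange and depressive symptoms secondary outcomes, and 17.1 models change in distress by treatment group. A sustained average worsening under CtP would be examined in a randomized comparison.

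It can also be said that the threshold is written for medical issues called unrelated to the study, that the survey exclusions concern responses alone, and that the broadest exclusion sits in an item about routine encounters. This ambiguity is real. Even on the kinder reading, no listed category brings procedure-related distress in, so the text still needs reconciling.

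The distress outcomes do not close the gap either. They are measured at baseline, 3 and 6 months and may miss a transient upset at a session. The annual monitoring report in 18.3.2 lists adverse events, serious events, deaths and deviations, with no distress outcomes.

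The objection on timing stands. Section 5.1 ends Phase II recruitment on 12/1/2021. Six months of follow-up, including the waitlist extension, takes scheduled surveys to about June 2022, and the latest listed revision is dated 4/28/23. A rule change cannot recover episodes that nobody wrote down.

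**Conclusion.** The concern holds in this form: the recording threshold is narrower than the definition the protocol adopts, leaves nearly all Mild events unrecorded, and gives sub-threshold distress from study procedures no route to the log except PI discretion. A low adverse-event count cannot by itself support a statement about mild or psychological harm.

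The conclusion assumes that staff apply the rules as written and that discretion is not used systematically. It does not depend on any assumed event rate, and the number of missed events cannot be estimated from the documents. The randomized distress outcomes limit the damage but do not replace event capture. The change is worth making because the results feed a larger trial.

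**What to change.** In 18.1.2, reconcile the definition, the three-part threshold, the 3- and 6-month question, the list of exclusions and the severity scale. Keep the threshold for intercurrent medical events unrelated to the study. Add that distress arising during a CtP session or a survey, or attributed by the caregiver to either or to the CtP recommendations, is recorded as an adverse event and graded on the existing scale, Mild included.

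In reporting, compare survey-related distress by arm. Report CtP-session distress descriptively for the CtP arm only: controls have no session during the randomized period, so a between-arm comparison would reflect unequal opportunity to record it. State the threshold in the safety summary and show distress and CES-D change by arm beside the counts.

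For participants already followed up, tabulate any documented upset or crisis consultations and state the limit on the safety conclusion.

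The cost is a short protocol edit, a few more adverse-event forms and a less favourable count. For completed follow-up, only the tabulation and the caveat remain possible.
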